## Introduction

### Scope

This document is a supplement to the MI-NAV protocol (ClinicalTrials.gov Identifier: NCT03871712) and comprises a statistical analysis plan (SAP) for the article “Modifiable prognostic factors of high costs related to healthcare utilization and productivity loss among people on sick leave due to musculoskeletal disorders - an external validation study”. The current SAP has been written after data collection was finished. However, the SAP will be uploaded to ClinicalTrials.gov before we enter the study database for the subsequent analyses.

## Administrative information

### Version of SAP

1.0

### Study sponsor

This study is part of the MI-NAV project, a large-scale project funded by the Research Council of Norway, through the program “Sickness absence, work, and health” (280431/GE).

## Study aim

The primary aim of this study is to assess the external validity of identified associations found between predefined modifiable prognostic factors and high costs related to healthcare utilization and productivity loss among people on sick leave due to musculoskeletal disorders, in the work package 3 (WP3) of the MI-NAV project. A secondary aim is to assess the external validity of identified associations found between predefined modifiable prognostic factors and high costs related to separately 1) healthcare utilization, and 2) productivity loss.

## Method

### Design and setting

This study contains secondary analyses embedded in a three-arm, pragmatic randomised controlled trial (RCT) with 6 months of follow-up, conducted within the Norwegian Labour and Welfare Administration (NAV); the WP3 [1] of the MI-NAV project (ClinicalTrials.gov Identifier: NCT04196634). In the current study, all included participants will be pooled into one sample.

### Study population, recruitment, stratification, randomization, and interventions

Eligible participants were workers, aged 18 to 67 years, on sick leave (50-100% sick leave rate,  $\geq 7$  consecutive weeks) due to musculoskeletal disorders (diagnosis within the musculoskeletal (L) chapter of the International Classification of Primary Care, 2nd edition (ICPC-2) [2]). Exclusion criteria were serious somatic or mental health disorders affecting work ability and entailing specialised treatment (e.g., cancer, psychotic disorders), pregnancy, unemployed, freelancers and self-employed workers, and insufficient Norwegian or English language skills to answer questionnaires or communicate by telephone. Participants were individually recruited through a phone call from NAV between April 2019 and October 2020. Every week recruiters received a list of eligible participants affiliated to eight NAV officers in South-Eastern Norway. All included participants signed an electronic informed consent form before study enrolment and were informed that they could withdraw at any time.

The Örebro Musculoskeletal Pain Screening Questionnaire Short Form (ÖMPSQ-SF) [3] and the Keele STarT MSK Tool (STarT MSK) [4] were used to stratify participants into risk groups of long-term sick leave [1, 5]. After stratification, participants were randomly allocated to either usual case management (UC), motivational interviewing (MI) and UC, or a stratified vocational advice intervention (SVAI) and UC, with a 1:1:1 allocation within each stratum of low/medium and high-risk.

A detailed description of the rationale, development and content of the interventions can be found elsewhere [1, 5]. Briefly, all participants were offered UC for people on sick leave in Norway. In addition, participants in the MI arm were offered 2 face-to-face sessions of MI from a NAV caseworker. Participants in the SVAI arm were offered vocational advice and case management from physiotherapists. Those stratified to the low/medium-risk group were offered 1-2 telephone sessions. Participants in the high-risk group were offered 3-4 sessions.

### Data collection, outcome, modifiable prognostic factors, and covariates

At baseline, all participants responded to an electronic questionnaire including demographic variables and a set of patient-reported measures. Data on healthcare utilization were collected from public records including the Norwegian Patient Registry (NPR) and the Municipal Patient and User Registry (KPR). Data on productivity loss were collected from public records (NAV), containing dates and grading of absenteeism, work assessment allowance, and disability pension, as well as the related diagnostic code, and contracted workhours. Data on healthcare utilization and productivity loss were collected in the period from baseline to 3 months retrospectively, and in the 6 months follow-up period. To assess representativeness of the study sample, we obtained anonymised registry data covering sex, age, occupation, and contracted work hours from all eligible candidates. All information

is stored and will be analysed securely through the Service for sensitive data (TSD) at the University of Oslo, Norway.

### *Outcomes*

The primary outcome of this study is costs related to healthcare utilization and productivity loss aggregated for 6 months of follow-up and dichotomized as high or low. Having high costs is defined as patients with costs in the top 25th percentile [6, 7]. As noted above, healthcare utilization was collected from public records (NPR, KPR) and included: primary healthcare use (general practitioner (GP), physiotherapist, chiropractor, and emergency room consultations) and secondary/tertiary healthcare use (outpatient contacts, day surgery, ordinary admission with overnight stay, and other admissions without overnight stay). Total cost of healthcare utilization per person will be estimated based on reimbursement rates collected from NPR and KPR. Productivity loss was collected from public records (NAV) and included productivity loss related to absenteeism, work assessment allowance, and disability pension. Total cost of productivity loss per person will be estimated based on number of days with productivity loss, adjusted for employment rate and grading of productivity loss, multiplied by an estimated average wage rate (from official statistics in Norway) including taxes and social costs. Healthcare utilization and productivity loss during the 6 months of follow-up will be described as shown in Table 2.

Secondary outcomes of this study are costs related to separately 1) healthcare utilization aggregated for 6 months of follow up and dichotomized as high and low, and 2) productivity loss aggregated for 6 months of follow up and dichotomized as high and low.

### *Modifiable prognostic factors*

Potential modifiable prognostic factors are factors expected to have the potential to be modified or improved by appropriate care or treatment, and therefore classified as modifiable. Potential modifiable prognostic factors of high costs related to healthcare utilization and productivity loss includes the following self-reported variables measured at baseline:

- Pain severity measured by the numeric rating scale (NRS) [8] from the STarT MSK [4]
- Disability measured by a single item (Q3) from the EuroQol 5 dimensions (EQ-5D-5L) [9]
- Self-perceived health measured by a single item (Q6) from the EQ-5D-5L [9]
- Depressive symptoms measured by a single item (Q6) from the ÖMPSQ-SF [3]
- Sleep quality measured by a single item (Q4) from the ÖMPSQ-SF [3]
- Health literacy measured by a single item (Q12) from the Musculoskeletal Health Questionnaire (MSK-HQ) [10]
- Work satisfaction measured by a single item (0-10, 0 = not satisfied, 10 = satisfied)
- Long-lasting disorder expectation measured by a single item (Q6) from the STarT MSK [4]
- Return to work expectancy measured by a single item (Q8) from ÖMPSQ-SF [3]

### *Covariates*

Prognostic factor research may vary depending on context (time, place, healthcare setting) and characteristics of the study population. We therefore plan to adjust for potential covariates when evaluating the modifiable prognostic factors. Potential covariates include the following self-reported variables measured at baseline:

- Sex
- Age
- Education level measured as the highest education completed, and categorised into low vs. high (university level)
- Pain duration measured by a single item (Q1) from the ÖMPSQ-SF [3]
- Group allocation (UC, MI and UC or SVAI and UC)

In addition, the following public records variables will be included as covariates:

- Absenteeism-related diagnosis type at baseline collected from the NAV registry and categorized into “upper/lower limb conditions”, “back and neck conditions”, “joint/inflammatory conditions”, “injury or trauma” or “other MSK conditions”
- Total costs related to healthcare utilization during a period of 3 months prior to inclusion. Healthcare utilization prior to inclusion was collected from public records (NPR, KPR) as described above. Total costs of healthcare utilization will be estimated as described above
- Total costs related to productivity loss during a period of 3 months prior to inclusion [11, 12]. Productivity loss prior to inclusion was collected from public records (NAV) as described above. Total costs of productivity loss will be estimated as described above

#### *Other variables*

Included participants will also be described with respect to the following baseline characteristics: mother tongue, days of productivity loss prior to inclusion, and healthcare utilization prior to inclusion.

### **Sample size**

This study contains secondary analyses embedded in the MI-NAV project. Details on sample size calculation are provided in the MI-NAV protocol [1]. To determine statistical power of this study we used number of events per parameter (EPP) [13-17] and the rule-of-thumb of “10 events per parameter included” [18-21]. With a fixed sample size of 509 participants included in the MI-NAV project, we anticipate 127 participants to be in the top 25th percentile of costs and categorised as having high costs (yes/no) (events). An EPP of 10 will allow a maximum of 13 parameters to be included in the final multivariable prediction model.

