### *External validation analysis*

Univariable and multivariable binary logistic regression models will be used to external validate findings from the analysis within the MI-NAV WP2 material. Associations (crude and adjusted for selected covariates) between each predefined modifiable prognostic factor and costs related to 1) healthcare utilization and productivity loss, 2) healthcare utilization, and 3) productivity loss will be assessed. The cost score will be entered into the model as a dependent dichotomous variable (high cost defined as patients with cost in the top 25th percentile, yes/no). Non-linear relationships in the modelling process will be explored using cubic splines or multivariable fraction polynomials, as these are recommended approaches for modelling continuous prognostic factors in prognosis research [23]. The results will be presented as crude and adjusted odds ratios with 95% confidence intervals as shown in Table 4. The decision on whether findings from WP2 are replicated will be based on the size and direction of the association, the confidence interval, and the p-value for each of the predefined prognostic factors [24].

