Total			
Secondary/tertiary care			
Outpatient contact			
Day surgery			
Ordinary admission with overnight stay			
Other admissions without overnight stay			
Total			
Productivity loss			
Sick leave			
Work assessment allowance			
Disability benefits			
Total			
Total			

Cost related to productivity loss are calculated on basis of reported days with productivity loss, converted into a 5-day workweek, and adjusted for employment rate and grading of productivity loss. \*Bias-corrected and accelerated bootstrapping (1000 simulations).

**Table 4.** Binary logistic regression analyses; individual associations between modifiable prognostic factors and high costs

	High costs related to healthcare utilization and productivity loss		High costs related to healthcare utilization		High costs related to productivity loss	
	Crude OR (95% CI)	Adjusted OR* (95% CI)	Crude OR (95% CI)	Adjusted OR* (95% CI)	Crude OR (95% CI)	Adjusted OR* (95% CI)
Pain severity (NRS, 0-10)						
Self-perceived health (EQ-5D-5L, Q6, 0-10)						
Depressive symptoms (ÖMPSQ-SF, Q6, 0-10)						
Sleep quality (ÖMPSQ-SF, Q4, 0-10)						
Return to work expectancy (ÖMPSQ-SF, Q8, 0-10)						
Work satisfaction (0-10)						
Disability (EQ-5D-5L, Q3) (ref: no/slight problems)						
Moderate problems						
Severe problems/unable to do						
Health literacy (MSK-HQ, Q12) (ref: completely/very well understanding)						
Moderate understanding						
Slightly/no understanding						
Long-lasting disorder expectation (STarT MSK, Q6) (ref: no)						

EQ-5D-5L indicates EuroQol 5 dimensions; CI, confidence interval; MSK-HQ, Musculoskeletal Health Questionnaire; NRS, Numeric Rating Scale; ÖMPSQ-SF, Örebro Musculoskeletal Pain Screening Questionnaire Short Form; STarT MSK, Keele STarT MSK tool; Q, question number. \*Adjusted by sex, age, education level, absenteeism related diagnosis type, pain duration, and costs related to 1) healthcare utilization and productivity loss prior to inclusion, 2) healthcare utilization prior to inclusion, or 3) productivity loss prior to inclusion.

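### At 10 events per parameter, 127 events allow at most 12 parameters, not 13, and the limit is attached to a prediction model that the SAP does not plan

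*SAP*

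**What the plan says.** The Sample size section of the SAP takes a fixed sample of 509, defines high cost as the top quarter, expects 127 events and adopts 10 events per parameter (EPP). It introduces the calculation with "To determine statistical power of this study we used number of events per parameter (EPP" and ends with "An EPP of 10 will allow a maximum of 13 parameters to be included in the final multivariable prediction model".

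The analysis itself is described elsewhere:

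- **External validation analysis** plans, for three cost outcomes, "Associations (crude and adjusted for selected covariates) between each predefined modifiable prognostic factor and costs related to". It adds: "Non-linear relationships in the modelling process will be explored using cubic splines or multivariable fraction polynomials".
- **Table 4** is titled as showing "individual associations between modifiable prognostic factors and high costs", with one crude and one adjusted odds ratio per factor (per category for disability and health literacy) and outcome.
- **Covariates** opens its first list with "Potential covariates include the following self-reported variables measured at baseline". That list ends with "Group allocation (UC, MI and UC or SVAI and UC". The second list, introduced by "In addition, the following public records variables will be included as covariates", contains diagnosis type, prior healthcare costs and prior productivity-loss costs.
- **The Table 4 footnote** adjusts for sex, age, education, diagnosis type, pain duration and prior costs of the kind that matches the outcome. It does not mention group allocation.

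**The concern.** There are two problems with the one sentence that says how many terms this analysis can carry.

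First, the number does not follow from its inputs. Under a rule that sets a minimum ratio, the permitted count is rounded down; 13 appears only if 12.7 is rounded up.

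Second, the limit is set for a model that is not planned. The SAP describes no step that builds one combined model from the nine factors. It judges replication factor by factor, on the size, direction, confidence interval and p-value of each association. The models to be fitted are per-factor adjusted models, and the SAP does not count their parameters. The count depends on a covariate set that is described in two ways, with no selection rule to connect them.

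An analyst who follows the SAP would therefore accept a 13-parameter model as meeting the rule when it does not. Whether any model reaches 13 depends mainly on whether allocation enters and whether the two prior costs enter separately, both of which are left open.

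**Working it through.** **Inputs (SAP, Sample size):** 509 participants, top 25% as events, EPP of 10.

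**Step 1: events.** 509 × 0.25 = 127.25, so 127. This reproduces the SAP's figure.

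**Step 2: maximum parameters.** 127/10 = 12.7, so 12 whole parameters.

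- 12 parameters: 127/12 = 10.58, rule met.
- 13 parameters: 127/13 = 9.77, rule missed.
- Using 127.25 or 128 events gives 12.725 or 12.8, still 12 after rounding down.
- Thirteen parameters need 13 × 10 = 130 events, which is 130/0.25 = 520 participants. The sample is fixed at 509.

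**Step 3: size of the adjusted models actually planned.** Continuous terms are taken as linear.

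- Sex 1, age 1, education 1 (two classes), diagnosis 4 (the five classes in Covariates): 7 in total.
- Pain duration: 1 if entered as a score, 2 if entered in the three classes of Table 1.
- Prior cost: 1 if combined or matched to the outcome, 2 if both kinds enter separately.
- Group allocation: 2 (three arms) if included.
- Prognostic factor: 1, or 2 for disability and for health literacy (Table 4).

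| Covariate set | Sum | Parameters | EPP |
|---|---|---|---|
| (a) Footnote set, one prior cost | 7 + (1–2) + 1 + (1–2) | 10–12 | 12.7–10.6 |
| (b) Footnote set, two prior costs | 7 + (1–2) + 2 + (1–2) | 11–13 | 11.5–9.8 |
| (c) Footnote set plus allocation, one prior cost | 7 + (1–2) + 2 + 1 + (1–2) | 12–14 | 10.6–9.1 |
| (d) All covariates, two prior costs | 7 + (1–2) + 2 + 2 + (1–2) | 13–15 | 9.8–8.5 |

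Set (a) covers both secondary outcomes, and the primary outcome if the two prior costs are combined. It meets the rule with 0 to 2 parameters to spare. Set (b) applies to the primary outcome; it misses only for disability and health literacy, and only with pain duration in three classes. Set (c) misses for those two factors in any case, and for all nine if pain duration has three classes. Set (d) misses for all nine.

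Spline or fractional polynomial terms would add to every row. So would the seven diagnosis classes shown in Table 1, by 2 parameters.

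**The case against.** The strongest reply is that little follows from the error. The Table 4 footnote is the only place that ties an adjustment set to the reported odds ratios. With one prior-cost term that set needs 10 to 12 parameters, so the rule is met whether the limit is 12 or 13. Even with two prior costs, the worst case is 13 parameters for two of the nine factors in the primary outcome. The larger shortfalls need group allocation, which the footnote leaves out. The Covariates list can naturally be read as candidates and the footnote as the final set. The SAP does plan multivariable models, so the mention of a prediction model may be loose wording, and the limit can be applied to each adjusted model. The ratio is itself called a rule of thumb.

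Most of this stands as an argument about size, and it is why the point is minor. It does not rescue the figure, since the sentence states a maximum at an EPP of 10. Nor does it settle the covariates. The SAP nowhere says that the footnote is the final set. Its firm statement that both prior costs will enter does not fit secondary models that carry only the matching one, and nothing explains why allocation drops out. It is also fair to say that the low end of each range assumes pain duration as a single score, which the SAP does not state.

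**Conclusion.** The concern holds and is minor. The stated maximum of 13 should be 12. The limit should refer to the per-factor adjusted models, whose size the SAP neither counts nor fixes. Under the readings the SAP leaves open, these models run from 10 to 15 parameters, an EPP of 12.7 down to 8.5.

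The arithmetic in steps 1 and 2 rests only on the SAP's own figures. The model counts assume five diagnosis classes, linear continuous terms, pain duration as one or two parameters, and 127 events for each of the three outcomes. The effect on the estimates is likely to be small, because 9.77 is close to 10 and the threshold is only a rule of thumb. Describing the ratio as a measure of statistical power is a matter of terminology and adds no weight.

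**What to change.** 1. In Sample size, replace the closing sentence with one to this effect: *127 events and an EPP of at least 10 support no more than 12 parameters in each adjusted model, with one model per prognostic factor.* If 13 is to be kept, state it with its true ratio of 9.8.
2. Reconcile Covariates with the Table 4 footnote into one covariate set. Say whether group allocation is in or out, and whether prior costs enter separately, combined or matched to the outcome.
3. State the parameter count and EPP of the resulting model, including the coding of pain duration and diagnosis and any non-linear terms.
4. As a wording change only, say that the ratio shows how many parameters the data can support, rather than that it determines power.

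The cost is SAP wording, with no new data and no change of method. The covariate set has to be fixed before the database is opened, which fits the timing that the SAP's Scope section sets for itself.

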### **Statistical analyses**

#### *General analysis considerations*

All analyses described in this SAP are considered a priori in that they have been defined in the protocol and/or in this SAP. All post hoc analyses will be identified as such in the article if relevant. All analyses will be carried out using SPSS, Stata, R, or other appropriate software, and controlled by a senior researcher/statistician. We consider our study as explanatory. Thus, no correction for multiple testing will be performed and p-values < 0.05 will be considered statistically significant. All statistical tests will be two-sided. All confidence intervals will be reported as 95%. Preliminary analyses assessing the influence of missing data and assumptions of normality for continuous variables will be conducted. The assumption of normal distribution will be investigated using histograms and QQ-plots. Normally distributed data will be presented with means and standard deviations (SDs), skewed data with medians and interquartile range (IQR). Categorical data will be reported as counts and percentages.

#### *Description of study flow*

The flow of participants through the study will be reported with a flow chart according to the REMARK guidelines [22]. Reasons for dropout will be provided where known. Differences between responders and non-responders will be evaluated.

#### *Missing data*

We anticipate few missing values within this study. Information on the primary and secondary outcome will be obtained from public records (NPR, KPR, NAV) where all individuals receiving any form of benefits are registered by their social security number. Furthermore, we anticipate few missing data for most of the potential modifiable prognostic factors and the covariates, as a requirement to answer all questions on key questionnaires was implemented in the electronic baseline questionnaire. Nevertheless, missing value pattern will be visually explored and handled by multiple imputation if relevant (if >5% data is missing).

### *Participant characteristics*

Baseline characteristics of included participants will be presented as shown in Table 1.

### *Healthcare utilization, productivity loss and cost estimation*

Type and frequency of use of different healthcare resources will be calculated for the 6-month follow-up period. Costs related to healthcare utilization will be estimated based on reimbursement rates collected from NPR and KPR. Days of productivity loss will be calculated for the 6-month follow-up period and adjusted for employment rate and grading of productivity loss. Costs related to productivity loss will be estimated based on number of days with 100% productivity loss and national average wage rates (from official statistics) in Norway including taxes and social costs. Healthcare utilization and productivity loss will be presented as shown in Table 2. All costs will be presented in euros (€) 2022 and estimated with both mean and median values with 95%CI, using bias-corrected and accelerated (BCa) bootstrapping as presented in Table 3. The BCa will be conducted with a bootstrap sample size of 1000. Cost data are commonly skewed, thus both mean and median values will be presented to support the result interpretation. Values in Norwegian kroner (NOK) will be recalculated to euros using the exchange rate from January 2022 (1€=NOK 10).

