EQ-5D-5L indicates EuroQol 5 dimensions; ICPC-2, International Classification of Primary Care 2ed edition; MSK-HQ, Musculoskeletal Health Questionnaire; NRS, Numeric Rating Scale; ÖMPSQ-SF, Örebro Musculoskeletal Pain Screening Questionnaire Short Form; STarT MSK, Keele STarT MSK tool. \*Absenteeism related diagnoses type at baseline, collected from the Norwegian Labour and Welfare Administration (NAV) registry. \*\*Collected from public records; the Norwegian Patient Registry (NPR) and the Municipal Patient and User Registry (KPR). \*\*\*Collected from the NAV registry, measured as calendar days, and adjusted for employment rate and grading of productivity loss.

**Table 2.** Healthcare utilization and productivity loss throughout 6-month of follow-up

	All participants (n=)	Missing, n (%)
Primary care		
Participants with primary care consultation, n (%)		
General practitioner		
Physiotherapist		
Chiropractor		
Emergency room		
No primary care consultation		
Numbers of consultations, median (IQR)*		
General practitioner		
Physiotherapist		
Chiropractor		
Emergency room		
Secondary/tertiary care		
Participants with secondary/tertiary care consultation, n (%)		
Outpatient contact		
Day surgery		
Ordinary admission with overnight stay		
Other admissions without overnight stay		
No secondary/tertiary care consultation		
Numbers of consultations, median (IQR)*		
Outpatient contact		
Day surgery		
Ordinary admission with overnight stay		
Other admissions without overnight stay		
Duration of ordinary admission with overnight stay in days, median (IQR)**		
Productivity loss		
Participants with productivity loss, n (%)		
Sick leave		
Work assessment allowance		
Disability benefits		
Duration of productivity loss in days, median (IQR)***		
Sick leave		
Work assessment allowance		
Disability benefits		

\*Calculated on basis of participants who have reported primary/secondary/tertiary care consultations. \*\*Calculated on basis of participants who have reported ordinary admission with overnight stay. \*\*\*Calculated on basis of participants who have reported productivity loss, converted into a 5-day workweek, and adjusted for employment rate and grading of productivity loss.

**Table 3.** Cost (€) due to healthcare utilization and productivity loss throughout 6-month of follow-up

	Participants with zero cost, n (%)	Mean (95%CI*)	Median (95% CI*)
Primary care			
General practitioner			
Physiotherapist			
Chiropractor			
Emergency room			

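### Does Table 3 need a stated fallback where the BCa interval for a median cost cannot be computed?

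*SAP*

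**What the plan says.** The SAP section on healthcare utilization, productivity loss and cost estimation has costs "estimated with both mean and median values with 95%CI, using bias-corrected and accelerated (BCa) bootstrapping as presented in Table 3". It fixes the number of resamples: "The BCa will be conducted with a bootstrap sample size of 1000". Its reason for giving two summaries is skewness: "Cost data are commonly skewed, thus both mean and median values will be presented to support the result interpretation". It does not discuss a large share of zeros.

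Table 3 lists four primary-care items, four secondary or tertiary items, three kinds of productivity loss, and totals. Each row has a mean and a median, both marked for BCa intervals. A further column, "Participants with zero cost, n" (%), shows that zeros are expected and will be counted.

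The Table 2 footnotes limit its medians to users; for consultations the wording is "Calculated on basis of participants who have reported primary/secondary/tertiary care consultations". Table 3 has no such restriction. Under Design and setting the SAP adds: "In the current study, all included participants will be pooled into one sample". The natural reading is that Table 3 medians cover all participants, although its header does not say so.

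**The concern.** A BCa interval needs two quantities from the data: a bias correction, from the share of resampled estimates below the observed one, and an acceleration, from the leave-one-out estimates. A median of 0 in non-negative data with a zero majority can leave both undefined, and more resamples do not help.

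A zero majority is plausible for day surgery, overnight admission, emergency room, chiropractor, work assessment allowance and disability benefits. It is unlikely for sick leave and the overall total, because everyone entered the study on sick leave.

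If those rows fail, the prespecified method leaves planned cells empty and someone must decide after seeing the data what to print. The candidates do not report the same thing: a percentile interval of 0 to 0 describes all participants, while a median among users describes a different group. The SAP also says its analyses are defined in advance, so a method that cannot be run in foreseeable rows looks like a specification error.

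**Working it through.** **Inputs.** From the SAP: n = 509 (Sample size), 1000 resamples, 95% intervals, all arms pooled. Assumed, because the SAP gives no figures: zero shares from 40% to 97%, and positive costs drawn from a lognormal(6, 1) distribution. Simulated cost values are therefore in arbitrary units.

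**The plan's own figure.** The only related count in the SAP is the expected number with high costs: 0.25 × 509 = 127.25, which agrees with 127. It is not in dispute.

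**Formulas.** With B resampled medians θ* and observed median θ:

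- bias correction z0 = Φ⁻¹(number of θ* below θ, divided by B);
- acceleration a = Σd³ / [6 (Σd²)^1.5], where d is the deviation of each leave-one-out median from their average.

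**Where the median becomes 0.** The middle rank is (509 + 1)/2 = 255, so the median is 0 from 255 zeros. A leave-one-out sample has 508 values, and its median averages ranks 254 and 255.

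- At 255 zeros, dropping a zero leaves 254 zeros, so rank 255 is positive and the leave-one-out median is above 0. Dropping a positive value leaves it at 0. There are two distinct values and a is defined.
- From 256 zeros, at least 255 zeros always remain. Every leave-one-out median is 0, every d is 0, and a = 0/0.

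**Bias correction.** No resampled median can be below 0. Counting strictly, the share below is 0 and z0 is minus infinity. If ties are half-counted, as scipy does, z0 stays finite: in one simulated data set per count it was about -0.55 at 256 zeros, -0.23 at 265 and -0.01 at 280. The infinite bias correction thus depends on the tie rule; the undefined acceleration from 256 zeros does not.

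**BCa limits for the median, 1000 resamples.**

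| Zeros of 509 | Share | R (boot) | scipy |
|---|---|---|---|
| 254 | 49.9% | 0 to 108.88 | finite (0 to 116) |
| 255 | 50.1% | error | 0 to 52.5 |
| 256 | 50.3% | error | not computable |
| 280 | 55.0% | error | not computable |
| 407 | 80.0% | error | not computable |

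The R and scipy columns use separate simulated data. Over 100 simulated data sets per count, scipy gave limits in all 100 at 250 and 254 zeros, and in none at 256, 280 and 402. With 10,000 resamples it still gave none at 256, 280 and 402.

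**What another method would recover.** A percentile interval has an upper limit above 0 only while P(resampled median > 0) = P(Bin(509, zeros/509) ≤ 254) is at least 0.025. This probability is 0.176 at 265 zeros, 0.034 at 275, 0.023 at 277 and 0.012 at 280. The percentile interval is therefore 0 to 0 from 277 zeros (277/509 = 54.4%). The order-statistic interval uses ranks 232 and 278 (coverage 95.9%) and is 0 to 0 from 278 zeros (278/509 = 54.6%). An informative all-participant interval is lost only from 256 to 277 zeros at most, that is 50.3% to 54.4%.

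**What remains.** The BCa interval for the mean was finite at every share tried: about 270 to 386 at 280 zeros, 106 to 198 at 407, and 9 to 37 at 494. The zero-cost count needs no bootstrap.

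**Downstream use.** The outcome is each participant's position in the top quarter of costs. The logistic models take that indicator, and replication is judged on their odds ratios, intervals and p-values. None of these uses a Table 3 interval.

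**The case for a change.** The best case for amending the SAP is that the failure is mathematical, foreseeable for several rows, confirmed in two programs, and curable with one sentence and a footnote. A plan that calls its analyses a priori should not leave the analyst to choose between a 0 to 0 interval and a users-only median once the zero shares are known. Table 2 already supplies a users-only convention.

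The arithmetic stands, and so does the observation that no fallback is written. The consequence is weaker. No substitute estimate is forced on anyone: printing the zero median without limits is enough, and it cannot bias an inference because none is drawn from that cell. Switching to a users-only median only in rows where the observed median is 0 would change the population within one column according to the data. Those rows could no longer be compared with the others or with the totals. It would also be imprecise for rare services: with 29 users in the simulation the median was 415 (306 to 570). Staying with all participants and using a percentile or order-statistic interval avoids that problem but gives 0 to 0 from about 55% zeros, which says little beyond the zero-cost share already planned.

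**Conclusion.** No change to the plan is needed. With 509 participants, BCa gives no interval for a median from 256 zeros in R and scipy (from 255 in R), so some Table 3 median cells probably cannot be filled as specified. The loss matters only in a band of about 50% to 55% zeros. Above that, any reasonable all-participant interval is 0 to 0. The gap shows itself in the output, sits in a descriptive table, and will be filled sensibly by marking the interval as not estimable or as 0 to 0. The zero-cost share and the mean with its interval carry the information for those rows, and no primary or secondary result depends on the choice.

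This rests on three assumptions. Table 3 medians are read as covering all participants, which the zero-cost column and the absence of a users-only footnote suggest but do not state; on a users-only reading the problem disappears. Zero majorities in the rarer components are plausible but not documented. SPSS and Stata, which the SAP also allows, were not checked and may treat ties or an undefined acceleration differently.
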